11.2 Sample size considerations

A sample size calculation has been carried out. Basis for this sample size calculation is preliminary data for the primary endpoint, the high frequency components of heart rate variability (median over one hour measurement per patient, further on denoted as HF). We assume a mean HF of about 49 ms^2 for the conventional mode of mechanical ventilation. An increase of on average 10 ms^2 (to 59 ms^2) for the variable pressure support mechanical ventilation is assumed. For sample size calculation, the standard deviation of the difference was set to 25 ms^2 .

Heartrate variability during mechanical pressure support ventilation – comparing

conventional and variable pressure support ventilation: a cross-over trial

When the sample size is 52, a single group t-test with a 0.05 two-sided significance level will have 80% power to detect the assumed effect.

Empirical knowledge of eventual intervention-related drop-out of patients from the study, leads to a sample size of 60 patients. (drop outs due to technological failure, emergency situation, unstable cardiovascular or pulmonary conditions, cardiac arrest and cardiopulmonary reanimation).

11.3 Relevant protocol deviations

Protocol deviations may occur if the treatment will be interrupted in case of technological failure, emergency situation, unstable cardiovascular or pulmonary conditions, cardiac arrest and cardiopulmonary reanimation. In case of a drop-out, the evaluation of the primary parameter is not meaningful, so that drop-outs will be excluded from the statistical analysis.

11.4 Statistical analysis plan

see 11.6

11.5 Missing, unused and spurious data

Missing, unused or spurious data due technological failure, emergency situation, unstable cardiovascular or pulmonary conditions, cardiac arrest and cardiopulmonary reanimation will be reported and presented. Records with missing data will be excluded from the analysis.

11.6 Endpoints analysis

11.6.1 Primary endpoint analysis

The median of the high frequency components (HF) measured over one hour per patient will be described descriptively separately for the two pressure support mechanical ventilation groups using means, standard deviations as well as medians and quantiles. Graphical illustration will be performed using boxplots.

To compare the mean HF between conventional and variable pressure support mechanical ventilation, first a paired t-test will be performed.

Furthermore, an ANOVA for repeated measurements, accounting for group (conventional vs. variable), randomization order, the interaction between group and randomization order as well as other influence factors (as gender and age) will be performed.

The significance level for the primary analysis is set to 0.05.

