
Alternative hypothesis of primary endpoint: there is a difference in the mean heartrate variability (measured as median high frequency components HF over a one hour measurement per patient) between variable/noisy pressure support mechanical ventilation compared to conventional pressure support mechanical ventilation.

Type-I and -II errors – power 
The significance level was set to 0.05. The study was planned to achieve 80% power.

Interim analysis 
No interim analysis.

Statistical methodology: 
The primary endpoint will be analysed using ANOVA for repeated measurements accounting for group of pressure support mechanical ventilation as well as randomization order, the interaction between group and randomization order as well as gender and age.

Sample size calculation: 
The study was planned based on preliminary data. When the sample size is 52, a single group t-test with a 0.05 two-sided significance level will have 80% power to detect the difference between a mean heartrate variability of 49 ms² in the conventional group and a mean

Heartrate variability during mechanical pressure support ventilation – comparing

conventional and variable pressure support ventilation: **a cross-over trial**

	of 59 ms^2 with variable pressure support mechanical ventilation assuming that the standard deviation of the difference is 25 ms^2 . Due to possible Drop-outs the sample size was set to 60 patients.
STUDY EXTENSION	If collection of data cannot be done in the given time.

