8. METHODOLOGY

The study will be performed for the time of HRV measurement (one hour conventional PSV followed by one hour variable PSV, in total two hours without interruption, randomized fashion).

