11.6.2 Secondary endpoint analysis

Similar to the main outcome parameters the median of the standard deviation of normal to normal (SDNN) and the median of high-frequency-low-frequency-ratios (HF-LF-ratio) over one hour measurements will be described descriptively with boxplots as well as means, standard deviations, medians and quantiles.

Furthermore, mean SDNN and HF-LF-ratio will be compared between treatment groups using paired t-tests. In addition, an ANOVA for repeated measurements, accounting for group, randomization order, the interaction between group and randomization order as well as other influence factors (as gender and age) will be performed.

The significance level for the secondary analyses is set to 0.05.

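### The synopsis and section 11.6.1 name different primary tests for HF, and the single 0.05 level is assigned to neither

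*Protocol*

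**What the plan says.** - **Synopsis, statistical methodology.** One analysis is named for the primary endpoint: "The primary endpoint will be analysed using ANOVA for repeated measurements accounting for group of pressure support mechanical ventilation as well as randomization order". The model also contains the group-by-order interaction, gender and age. No t-test is named as the analysis.
- **Section 11.6.1.** Two analyses appear. The first is "To compare the mean HF between conventional and variable pressure support mechanical ventilation, first a paired t-test will be performed". An ANOVA follows as a further step, adjusting for group, "randomization order, the interaction between group and randomization order as well as other influence factors (as gender and age) will be performed". Here gender and age are only examples, so the covariate list is open, whereas the synopsis list is closed.
- **Section 11.6.1, significance level.** "The significance level for the primary analysis is set to 0.05". The sentence does not say which of the two tests it governs.
- **Section 11.2.** The trial is sized on the t-test: "a single group t-test with a 0.05 two-sided significance level will have 80% power to detect the assumed effect". The synopsis repeats this basis.
- **Section 11.4.** It only refers the reader to 11.6.
- **Section 8.** The two ventilation modes are given "in total two hours without interruption, randomized fashion".
- **Section 11.6.2.** The same pair of tests is used for the secondary heart rate variability measures: "Furthermore, mean SDNN and HF-LF-ratio will be compared between treatment groups using paired t-tests", with an ANOVA in addition.

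**The concern.** A confirmatory claim needs one test fixed in advance. Here two tests are eligible, and the protocol gives no rule for the case where they fall on opposite sides of 0.05. A choice made after the data are seen could be driven by the result.

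The tests are not interchangeable. A paired t-test on the within-patient differences has no term for period. If HF drifts between hour 1 and hour 2, the drift enters the differences with opposite sign in the two sequences and inflates the error term. In a two-period, two-sequence cross-over the group-by-order interaction is the period effect, so the ANOVA can remove the drift, although the protocol does not label the term that way. At stake are an undeclared choice between two results and some avoidable loss of power. If the analysed sequences are unequal, the t-test estimate is also biased.

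**Working it through.** **Inputs from the protocol (section 11.2).** Mean difference 59 − 49 = 10 ms²; SD of the difference 25 ms²; two-sided 0.05; 80% power; 52 completers, raised to 60.

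**Assumptions.** The protocol gives no period effect, so π (hour 2 minus hour 1) is varied. It gives no allocation ratio, so 1:1 is assumed, with unequal splits tried as well. Data are normal, with no carry-over; gender and age are left out.

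**1. The planned figure.** For the paired t-test, df = n − 1 and the noncentrality is (10/25)·√n. At n = 51 power is 79.99%; at n = 52 it is 80.78%. The protocol's 52 is reproduced.

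**2. The period-adjusted test.** The estimate is the average of the two sequence-specific mean differences. Its standard error is (SD/2)·√(1/n₁ + 1/n₂), with df = n₁ + n₂ − 2.

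| Completers | Paired t-test | Period-adjusted |
|---|---|---|
| 52 (26/26) | 80.78% | 80.75% |
| 60 (30/30) | 86.2% | 86.1% |

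Adjustment costs one degree of freedom and almost no power.

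**3. Effect of a drift, sequences 26/26.** Differences (variable minus conventional) were simulated as N(δ + π, 25) in the conventional-first sequence and N(δ − π, 25) in the other. Here 25 is the SD net of period.

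| π (ms²) | Paired power (δ = 10) | Adjusted power (δ = 10) | Verdicts differ (δ = 10) | Paired type I error (δ = 0) |
|---|---|---|---|---|
| 0 | 81% | 81% | 0.5% | 5.0% |
| 5 | 80% | 81% | 1.3% | 4.5% |
| 10 | 76% | 81% | 4.6% | 3.6% |
| 20 | 62% | 81% | 19% | 1.2% |

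With balanced sequences the t-test stays unbiased. It becomes conservative because its estimated standard error absorbs the drift.

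**4. If SD 25 already contains the drift.** The residual SD is √(625 − π²): 24.5 at π = 5 and 22.9 at π = 10. Adjusted power is then 82% and 87%, and paired power about 81% and 83%. The t-test keeps its planned power; the adjusted test gains.

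**5. Unequal sequences.** Drop-outs are excluded (section 11.1), so the sequences can become unequal. The bias of the t-test estimate is π·(n₁ − n₂)/n.
- 28/24, π = 10: 10 × 4/52 = 0.8 ms².
- 30/22, π = 10: 10 × 8/52 = 1.5 ms².

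Both compare with a target difference of 10 ms². The adjusted estimate is unbiased.

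**6. Type I error if either test at p < 0.05 counts.** It is 5.0–5.1% at 26/26 and 5.0–5.5% at 28/24 (π from 0 to 20), and 5.7–7.5% at 30/22 (π from 0 to 15). The two tests are highly correlated, so the independent-tests figure, 1 − 0.95² = 9.75%, does not apply.

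**7. Which coefficient of the ANOVA is read.** The ANOVA adjusts for period only if the group effect is averaged over both sequences. With reference-level coding the group coefficient is the effect in one sequence, mixed with period. At 26/26 its false-positive rate is then 17%, 52% and 85% for π = 5, 10 and 15. The contrast must therefore be stated.

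**The case against.** The strongest reply is that the t-test is already primary. Section 11.6.1 puts it first and 11.6.2 keeps that order. The sample size in both 11.2 and the synopsis is based on it. On that view the synopsis sentence is an abbreviation and the ANOVA a supplement. This is a fair reading of 11.6.1, but it makes the synopsis wrong, since the only primary analysis named there is the ANOVA. The order word may also mean sequence rather than rank. The passages still have to be reconciled.

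It can also be said that naming either test would cure the contradiction, so preferring the ANOVA is a recommendation. Block randomisation (8.3) and replacement of withdrawn patients (7.3.2) limit imbalance, and a balanced t-test is unbiased and conservative. That stands. Omitting period is a matter of efficiency here and does not make the test invalid.

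The largest figures need a drift of 20 ms², twice the assumed treatment effect. At 0 to 5 ms² the loss is about one percentage point, and if SD 25 includes the drift the t-test keeps its planned power. This also stands.

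Finally, the open covariate list matters little for the primary result, because main effects of gender and age do not change the within-patient contrast. That is correct; closing the list is tidying.

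**Conclusion.** The point holds. The protocol fixes the primary test in two places and they disagree, and the one significance level belongs to neither test by name. Section 11.4 leads back to the same text.

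The consequence is moderate. Depending on an assumed drift of 0 to 20 ms², the two tests give different verdicts in 0.5% to 19% of trials at the planning values. Over the same range the t-test loses between nothing and about 19 percentage points of power. These figures rest on balanced sequences, normal data, no carry-over and an SD of 25 ms² net of period. Marked type I error inflation is not the issue: it is at most about 5.5% at 28/24 and reaches 7.5% only at a 30/22 split. This should be fixed before the data are analysed.

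**What to change.** Use the same text in the synopsis and in section 11.6.1, for example:

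> The single primary analysis is the treatment contrast (variable minus conventional) from a repeated-measures model for HF with treatment, period and sequence as fixed effects and patient as the random or repeated factor, tested two-sided at 0.05. The covariates are gender and age only. The paired t-test is a sensitivity analysis.

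Writing the model with an explicit period term replaces the group-by-order interaction, which is the same effect, and removes the coding problem. Close the covariate list in 11.6.1 to match the synopsis. State the same order of tests in 11.6.2.

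The cost is wording only. Power for the period-adjusted contrast is 80.75% with 52 completers and 86.1% with 60, so neither number changes. Splitting the level between the two tests is unnecessary and would be expensive: at 0.025 each, 62 completers would be needed for 80% power.

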11.6.2 Secondary endpoint analysis

Similar to the main outcome parameters the median of the standard deviation of normal to normal (SDNN) and the median of high-frequency-low-frequency-ratios (HF-LF-ratio) over one hour measurements will be described descriptively with boxplots as well as means, standard deviations, medians and quantiles.

Furthermore, mean SDNN and HF-LF-ratio will be compared between treatment groups using paired t-tests. In addition, an ANOVA for repeated measurements, accounting for group, randomization order, the interaction between group and randomization order as well as other influence factors (as gender and age) will be performed.

The significance level for the secondary analyses is set to 0.05.

11.6.3 Safety and tolerability endpoints

The occurrence of adverse events will be described descriptively by frequencies and percentages.

11.6.4 Exploratory analyses

All exploratory parameters, which are obtained from arterial blood gas analysis (systolic and diastolic arterial blood pressure, arterial partial pressure of oxygen, arterial partial pressure of carbon dioxide) will be described with descriptive statistics (boxplots, means, standard deviations, medians and quartiles) separately for the two groups.

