EXCLUSION CRITERIA	
patients aged < 18 or > 80 years
 
patients with active heart pace maker / defibrillator
 
patients with absent sinus rhythm in electrocardiogram
 
patients with known severe disease of autonomous nervous system
 
women, who are already known to be pregnant before taking part in this study

COMPARATIVE DEVICE	None.
CONCOMITANT MEDICATION/CON-COMITANT DEVICE	Every therapy / medication / monitoring is allowed as indicated per routine.
EFFICACY ENDPOINTS	
Primary study endpoint:
 
High frequency components (HF) of Heart Rate Variability (median over one hour measurement per patient)
 
Secondary study endpoints:
 
Applied tidal volumes and other heart rate variability parameters (standard deviation of R to R intervals (SDNN), high frequency to low frequency ratio),
 
Exploratory endpoints:
 
physiological parameters (systolic and diastolic arterial blood pressure, arterial partial pressure of oxygen, arterial partial pressure of carbon dioxide).

TOLERABILITY / SAFETY ENDPOINTS	The occurrence of adverse events will be documented.
QUALITY OF LIFE	No quality of life parameters will be measured.
STATISTICAL METHODOLOGY	
Primary Endpoint
 
High frequency components (HF) of Heart Rate Variability (median over one hour measurement per patient)

Secondary Endpoints 
Applied tidal volumes and other heart rate variability parameters (median of standard deviation of R to R intervals (SDNN) or high frequency to low frequency ratio over one hour measurement per patient)

Exploratory Endpoints 
Physiological parameters (systolic and diastolic arterial blood pressure, arterial partial pressure of oxygen, arterial partial pressure of carbon dioxide).

Null and alternative hypotheses: 
Null hypothesis of primary endpoint: there is no difference in the mean heartrate variability (measured as median high frequency components HF over one hour measurement per patient) between variable/noisy pressure support mechanical ventilation compared to conventional pressure support mechanical ventilation.

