5.2 Rationale of clinical investigation

In this interventional clinical study, we will apply, in a randomized fashion, conventional PSV and variable PSV each for a duration of one hour. During ventilation we will record all data of the patients monitor, including the electrocardiogram (ECG), which is routinely monitored in our patients, and respiratory data, to determine HRV parameters retrospectively. All other ventilatory, hemodynamic and pharmacological treatment will be part of the clinical routine. As two modes of ventilation will be compared, this study is an interventional clinical cross-over trial.

Primary study objective:

To compare the high frequency components (HF) of Heart Rate Variability (median over one hour measurement per patient) from ECG data between conventional and variable pressure support ventilation.

The following parameters will be measured and calculated:

- ECG waveform at 200 Hz
- Pulse pressure waveform as part of the clinical routine
- Arterial blood gas analysis at the beginning and end of each ventilation mode
 - Arterial partial pressure of oxygen (PaO_2)

Heartrate variability during mechanical pressure support ventilation – comparing conventional and variable pressure support ventilation: a cross-over trial

- Arterial partial pressure of carbon dioxide (PaCO₂)
- Arterial pressure waveform if part of the clinical routine
- All respirator data

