6.3 Exploratory Objectives

Comparison of change in Physiological parameters (systolic and diastolic arterial blood pressure, arterial partial pressure of oxygen, arterial partial pressure of carbon dioxide) between conventional and variable pressure support ventilation. In contrast to the primary and secondary parameters, the exploratory parameters are not measured during the whole study duration (one hour per treatment) but at the beginning and end of each treatment.

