7.2.2 Duration of the clinical investigation

The duration of the clinical cross-over trial is one year. First, subjects will be included in the clinical study according to inclusion and exclusion criteria. The order of the two interventions will be randomized. According to the randomization, subjects will be allocated first to conventional PSV (duration one hour) then to variable PSV (one hour) or vice versa. Thereafter, the study observation period will be over. Subjects will not have to come to follow up visits or investigations.

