8.4 Blinding

No blinding procedure will be performed. The patient will be blinded, with respect to the respiratory-treatment, due his medical status.

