8.6.4 Laboratory Tests

Blood gas analysis will be taken at the beginning and the end of each treatment (2 times 2 arterial blood gas analyses, in total 4 blood gas analyses per patient).

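### Minor, exploratory only: PaO2 is compared between modes without relation to inspired oxygen, so oxygen adjustments that depend on the mode can distort the comparison

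*Protocol*

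**What the plan says.** The exploratory objective in Protocol 6.3 reads "Comparison of change in Physiological parameters (systolic and diastolic arterial blood pressure, arterial partial pressure of oxygen, arterial partial pressure of carbon dioxide", compared between conventional and variable pressure support. Section 8.6.4 fixes the sampling: "Blood gas analysis will be taken at the beginning and the end of each treatment", which makes four samples per patient. Section 11.6.4 then states "arterial partial pressure of oxygen, arterial partial pressure of carbon dioxide) will be described with descriptive statistics", separately for the two groups. It plans no test and does not mention change.

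On everything else done to the patient in the two hours, section 5.2 says "All other ventilatory, hemodynamic and pharmacological treatment will be part of the clinical routine", and the synopsis adds "Every therapy / medication / monitoring is allowed as indicated per routine". Section 8.4 says "No blinding procedure will be performed"; only the patient is described as unaware of the mode. On sequence, section 7.2.2 says "The order of the two interventions will be randomized", and section 8 has the two hours follow each other without a break.

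The inspired oxygen fraction does not appear anywhere in the protocol. Section 5.2 lists the complete respirator record among the data to be collected, but no analysis refers to it.

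**The concern.** PaO2 depends on how well the lung exchanges gas and on how much oxygen is supplied. The protocol wants to know whether the mode changes the first, and leaves the second to routine under staff who know the mode. If the oxygen setting is changed more often, or in a different direction, under one mode than under the other, the PaO2 comparison mixes the effect of the mode with the clinicians' response to it. A reader of the exploratory table could then take a difference in oxygen setting for a difference in gas exchange, or overlook a real one. What is at stake is the interpretation of one exploratory parameter.

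**Working it through.** **The plan's own figure.** The protocol states no number for PaO2, so there is none to reproduce for this endpoint. Its one calculation concerns HF: difference 10 ms², standard deviation of the difference 25 ms², two-sided 0.05. It reproduces. Power by the noncentral t is 0.7999 at 51 patients and 0.808 at 52. PaO2 plays no part in it.

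**Step 1: which oxygen changes enter the comparison.** Write PaO2 = R × F, with R the PaO2/FiO2 ratio and F the inspired oxygen fraction. Hold R constant to represent unchanged gas exchange (an approximation). The start-to-end change within a mode is then R × (F_end − F_start).

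- F differs between the hours but is constant within each: the change is zero in both hours, so the change score is clean. The levels still differ, and section 11.6.4 as worded describes levels.
- F is altered between the start and end samples of an hour: the end level and the change both move by R × step.
- F is altered in the first hour and left there: the first-hour change contains the step, and the second-hour levels contain it throughout.
- F is altered in response to the end sample of the first hour: the step falls in the second hour. It enters the levels, and it enters the change if made after that hour's start sample.

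**Step 2: which of these bias the comparison.** Order is randomised, so a change unrelated to mode falls equally often on either mode in expectation and adds only noise. A change that depends on the mode arises after randomisation, and the order does not cancel it.

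**Step 3: direction.**

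- Masking: gas exchange improves under a mode and oxygen is lowered in the same hour, before the end sample.
- Exaggeration: variable support comes first and raises PaO2, and oxygen is then lowered during the conventional hour.
- Creation: staff adjust oxygen because they know the mode, with gas exchange unchanged.

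**Step 4: size.** None of these inputs is in the documents; all are assumptions: R of 150 to 300 mmHg, a step of 0.05 or 0.10, and 10% to 50% of patients adjusted in one mode only and in the same direction.

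Shift per adjusted patient = R × step. Shift of the mean difference = share × R × step.

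| Step | R (mmHg) | Per adjusted patient (mmHg) | Mean, 10% adjusted | Mean, 50% adjusted |
|---|---|---|---|---|
| 0.05 | 150 | 150 × 0.05 = 7.5 | 0.75 | 3.75 |
| 0.05 | 300 | 300 × 0.05 = 15 | 1.5 | 7.5 |
| 0.10 | 150 | 150 × 0.10 = 15 | 1.5 | 7.5 |
| 0.10 | 300 | 300 × 0.10 = 30 | 3.0 | 15 |

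A 0.05 step thus moves the mean between-mode difference by 0.75 to 7.5 mmHg with no effect of the mode, and a 0.10 step by 1.5 to 15 mmHg.

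**The case against.** A reader might infer that the comparison cannot separate mode from oxygen setting at all, and that titration always works against a true effect and may reverse its sign. The documents do not support that.

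- *Timing.* The study samples are taken at the start and end of each mode. A mode's effect first shows in its own end sample, when that mode's PaO2 has already been measured. A study blood gas therefore cannot reveal the current mode's gain in time to hide it in the same hour; that needs another trigger, such as continuous monitoring or an additional clinical sample. A response to the first end sample falls in the second hour and can exaggerate a difference as well as mask one. This stands.
- *Change score.* Section 6.3 speaks of change, most naturally from start to end of each mode, and that removes any setting constant within an hour. This stands, but it does not remove a change made within the hour, and section 11.6.4 does not carry the change through.
- *Randomised order.* It balances adjustments unrelated to mode. This stands; only mode-dependent adjustments bias the result.
- *Complete masking.* One can construct a patient whose gain disappears: at F = 0.40 and R = 200, PaO2 is 80 mmHg; if R rises to 229 while F falls to 0.35, PaO2 is still 80 (80 / 0.35 = 229). That is one patient on assumed values. For the mean to be hidden in this way, every patient would need such a step in one mode only, and the documents give no titration frequency.
- *Pragmatic reading.* PaO2 under a mode plus routine care is a legitimate description, and the ratio is not fully independent of inspired oxygen. Both are true, and they argue for adding the ratio beside raw PaO2 and not for replacing it.
- *Detail for an analysis plan.* A separate plan may exist, but section 11.4, which bears that title, only refers to 11.6. The point concerns the parameter chosen in 6.3 and 11.6.4, not an omitted detail.

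**Conclusion.** The point holds as a minor one. PaO2 is used without relation to inspired oxygen while that setting is uncontrolled and staff know the mode, so mode-dependent adjustments can mask, exaggerate or create a between-mode difference. Under the stated assumptions with a 0.05 step, the mean difference shifts by about 0.75 to 7.5 mmHg without any mode effect; the true size could be nil if adjustments are rare or unrelated to mode.

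Two inferences underlie this: that routine ventilatory treatment includes changing inspired oxygen, and that the respirator record contains the setting. Both are natural readings of broad wording, but the protocol states neither. The endpoint is exploratory and descriptive, with no test and no part in the sample size, so the primary HF conclusion is untouched.

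**What to change.** In 6.3 and 11.6.4, add PaO2 divided by the inspired oxygen fraction at each of the four blood gases, taking the fraction from the recorded respirator data (assuming they include it). Describe it by mode as level and as start-to-end change. Show beside it raw PaO2, inspired oxygen, and the number of patients whose oxygen setting changed in each mode.

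The cost is one derived variable and a small edit to each of the two sections; no procedure is added. Because the ratio is not fully independent of inspired oxygen, the raw values stay in the table. The oxygen setting itself remains a clinical decision, and nothing here restricts it.

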2. SYNOPSIS OF THE CLINICAL INVESTIGATION

TITLE	Heartrate variability during mechanical pressure support ventilation – comparing conventional and variable pressure support ventilation: a cross-over trial					
ACRONYM	Heartrate variability during variable pressure support mechanical ventilation					
NAME OF DEVICE	Infinity Delta Monitor, Dräger, Lübeck, Germany Evita Infinity V500, Dräger, Lübeck, Germany					
DESCRIPTION OF THE PROCEDURES	Retrospectively determine heart rate variability from a standard electrocardiogram (Infinity Delta Monitor) recorded during conventional and variable pressure support mechanical ventilation (Evita Infinity V500). We hypothesize that heartrate variability (median of high frequency components over one hour) will increase during variable pressure support mechanical ventilation as compared to the conventional mode of mechanical ventilation.					
OBJECTIVES	
Primary study objective:
 
To compare the High frequency components (HF) of Heart Rate Variability (median over one hour measurement per patient) between conventional and variable pressure support ventilation.
 
Secondary study objectives:
 
Comparison of applied tidal volumes and in heart rate variability parameters (median of standard deviation of R to R intervals (SDNN), median of high frequency to low frequency ratio over one hour measurement per patient) between conventional and variable pressure support ventilation.
 
Exploratory objectives:
 
Comparison of change in physiological parameters (e.g. systolic and diastolic arterial blood pressure, arterial partial pressure of oxygen, arterial partial pressure of carbon dioxide) between conventional and variable pressure support ventilation.
					
TYPE OF THE INVESTIGATION	Interventional MPG § 40.3 cross-over trial					
PERIOD OF ENROLMENT	First patient First visit	1Q	Last patient First visit	3Q	Last patient Last visit	3Q
CENTER(S) / COUNTRY(IES)	1 center (Medical University of Vienna), Austria					
PATIENTS / GROUPS	60 patients					

Heartrate variability during mechanical pressure support ventilation – comparing

conventional and variable pressure support ventilation: **a cross-over trial**

INCLUSION CRITERIA	
patients undergoing therapy at an ICU
 
patients aged between 18 and 80 years
 
patients intubated and ventilated using SPN-CPAP/PS ventilator mode
 
patients with sinus rhythm in electrocardiogram

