8.2.10 Concomitant medication

All concomitant medications are allowed.

8.2.11 Interactions, reverse reactions and side effect of the medical device:

Not applicable. All devices used are part of the clinical routine ICU therapy. Both the conventional and variable PSV modes are part of the clinical routine ICU therapy. The arterial blood gas analyses are not part of the clinical routine ICU therapy. Potential risks and side effects of taking arterial blood gas analyses include infection and bleeding only in case of inappropriate usage.

8.3 Randomization and stratification:

Subjects will be randomized to the order of conventional and variable PSV treatment (first conventional PSV and then variable PSV or first variable PSV and then conventional PSV). The randomization will be performed by block-randomization using the online randomization program of the Medical University of Vienna (<https://www.meduniwien.ac.at/randomizer/web/login.php>). There will be no stratification of subjects studied. Only the statistician ([name]) and the responsible person performing measurements ([name]) will have access to the online randomization program.

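### The exploratory objective compares change between modes, but 11.6.4 only summarises each mode separately, so the precision of the within-patient difference is never reported

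*Protocol*

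**What the plan says.** Section 6.3 of the protocol gives the exploratory objective as "Comparison of change in Physiological parameters", meaning systolic and diastolic pressure, PaO2 and PaCO2, with the two ventilation modes set against each other. The synopsis opens its own version the same way: "Comparison of change in physiological parameters". Section 6.3 adds that the "exploratory parameters are not measured during the whole study duration (one hour per treatment) but at the beginning and end of each treatment", which gives four values per patient and parameter.

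Section 8.3 sets the design: "Subjects will be randomized to the order of conventional and variable PSV treatment". Every analysed patient therefore contributes to both modes.

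Section 11.6.4 is the whole analysis text for these parameters. It states that they "will be described with descriptive statistics (boxplots, means, standard deviations, medians and quartiles) separately for the two groups". It mentions no change score, between-mode contrast, within-patient difference or interval. Section 11.4, headed as the statistical analysis plan, only refers the reader to 11.6.

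The neighbouring sections do use the pairing. For the primary endpoint, 11.6.1 follows the per-mode descriptives with a contrast: "first a paired t-test will be performed". For the secondary heart rate variability endpoints, 11.6.2 states that "mean SDNN and HF-LF-ratio will be compared between treatment groups using paired t-tests". Both then add a repeated-measures ANOVA.

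**The concern.** The objective is a comparison of the two modes; the stated analysis is two separate descriptions. In a cross-over the information about the difference lies within patients. Two sets of means, SDs, quartiles and boxplots mainly show how patients differ from each other, and do not show how consistently each patient moved from one mode to the other.

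At stake is how an exploratory result is read. A reader who judges the between-mode difference against the per-mode SDs uses the wrong yardstick. PaO2 and PaCO2 are the only gas-exchange endpoints listed, and sections 8.6.3 and 8.6.4 require four arterial samples per patient, beyond routine care, to obtain them. It is reasonable to expect the analysis to deliver the comparison that those samples are meant to serve.

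**Working it through.** **1. The plan's own figure.** Section 11.2 gives a mean difference of 10 ms², an SD of the difference of 25 ms², two-sided alpha 0.05 and 80% power. With the noncentral t distribution for a paired test, the smallest n is 52 (power 80.8%). The normal approximation gives (1.960 + 0.842)² × 25² / 10² ≈ 49.1, so 50. The stated 52 reproduces. It rests on the SD of the within-patient difference, which is the quantity that 11.6.4 would not yield for the exploratory parameters.

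**2. What per-mode summaries contain.** Write C and V for a patient's value under conventional and variable support.

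- Mean difference: mean(V − C) = mean(V) − mean(C) when the same patients supply both. The analysis set in 11.1 requires treatment with both modes, and 11.5 excludes records with missing data, so this should hold. The average shift is recoverable.
- Spread of the difference: SD²(V − C) = SD²(V) + SD²(C) − 2ρ·SD(V)·SD(C). The correlation ρ appears in neither summary, so the SD and the confidence interval are not recoverable. Nor are the individual shifts.

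**3. Raw levels.** Assume equal SDs in the two modes and n = 52 pairs.

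- SE treating the modes as separate groups: SD·√(2/n)
- SE from pairs: SD·√(2(1 − ρ)/n)
- Ratio: 1/√(1 − ρ)

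The protocol gives neither an SD nor ρ for these parameters, so ρ is an assumed range and half-widths are in units of the between-patient SD. The separate-group 95% half-width is 0.389 throughout.

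| assumed ρ | SE ratio | paired 95% half-width | half-width ratio (t quantiles) |
|---|---|---|---|
| 0.5 | 1.41 | 0.278 | 1.40 |
| 0.7 | 1.83 | 0.216 | 1.80 |
| 0.8 | 2.24 | 0.176 | 2.21 |
| 0.9 | 3.16 | 0.125 | 3.12 |

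At ρ = 0 the half-width ratio is 0.99, so nothing is lost.

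**4. Start-to-end change.** This is the quantity named in 6.3, and it behaves differently. Take a stable patient effect plus an occasion error of variance σ² at each of the four measurements.

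- The patient effect cancels in each change, and each change has variance 2σ².
- With independent errors the two changes are uncorrelated: ρ = 0, ratio 1.
- Section 8 runs the two hours without interruption, so the end of the first mode adjoins the start of the second. If those two errors correlate at r, the covariance of the changes is −rσ², and ρ = −rσ²/(2σ²) = −r/2.
- At the extreme r = 1, ρ = −0.5 and the ratio is 1/√1.5 ≈ 0.82. Separate summaries would then suggest a standard error that is too small.

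**The case against.** The strongest reply is that these endpoints are exploratory, that 11.6.4 sets no hypothesis or test, and that description by mode is also the first step for the primary endpoint. Which exploratory summaries to tabulate is often left to an SAP, and the paired data are collected, so the difference can be computed at any time. Much of this stands, and it is why the point is minor. It does not remove the point: 11.4 names 11.6 as the analysis plan, and 11.6.4 fixes an analysis that does not deliver the comparison set in 6.3.

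Two stronger readings are tempting and are not supported.

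- A reader might infer that separate summaries conceal the size of the difference. They do not: with complete pairs, as 11.1 and 11.5 provide, the difference of the two means is the mean paired difference.
- A reader might infer that a real shift is always swamped by between-patient spread, whichever value is summarised. That can happen for raw levels. For change, the stable patient level has already cancelled, and separate summaries may be about right or may overstate precision.

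How readers would interpret overlapping boxplots is conjecture, and the point does not depend on it.

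**Conclusion.** The mismatch is real but minor. Sections 2 and 6.3 promise a between-mode comparison of change; 11.6.4 as written gives the average shift by subtraction only, with no SD, no interval and no view of individual patients.

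For raw levels, a standard error judged from separate summaries is about 1.4 to 3.2 times too large at an assumed ρ of 0.5 to 0.9. For change scores the ratio may be 1, or as low as about 0.82 under the simple error model above. The multipliers rest on assumed correlations and equal SDs, none of which the protocol gives. That separate summaries leave the precision of the difference unknown needs no such assumption.

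No primary or secondary conclusion, sample size or error rate is affected. Severity is low.

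**What to change.** Keep the per-mode descriptives in 11.6.4 and add, for each exploratory parameter:

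- the end-minus-start change in each mode, and the within-patient difference of those changes (variable minus conventional);
- the within-patient difference of the end-of-mode values (variable minus conventional);
- for each of these two differences, the mean, SD and 95% CI, overall and by randomised order;
- a plot joining each patient's paired values.

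Stating which of the four values are differenced matters, because the two contrasts can have quite different precision. Label the results exploratory, with no significance claim.

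The change needs a sentence or two in the protocol and a few lines of code on data already collected. It needs no further patients, samples or tests. The downside is a slightly longer results table.
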